The most common sensory perceptual abnormality is auditory sensory over-responsivity (SOR). SOR is characterized by a quicker, more intense, and/or longer duration response to sensation than those with typical sensory responsivity (Miller et al., 2007). Children with ASD can have abnormal and often severe behavioral reactions to a variety of sounds in their everyday environment (Doman & Lucker, 2015). The fight or flight response elicited by auditory SOR increases maladaptive behavioral responses in a variety of environments and negatively impacting adaptive living skills. Adaptive life skills are everyday skills needed to function and meet the demands of one's environment, including independent self-care and social interaction.

Modification / Update, MOD006-STU-2019-1698, [name], 4/12/2025

Given the increased prevalence of ASD and the heightened awareness of sensory over- and under-responsivity (SOR) (SUR), particularly to auditory input, as a component of ASD, there is a growing need for evidence-based treatments to relieve discomfort and lessen behavioral reactions to a variety of every day environmental sounds to support improved adaptive life skills.

The objective of this study is to investigate changes in adaptive life skills and behavioral responses in children with ASD using Advanced Brain Technology's Listening Program® Spectrum music utilizing Waves™ (bone conduction) headphones.

The information obtained will contribute to a more comprehensive and evidence-based approach to the treatment of auditory SOR in children with ASD. It is expected that reducing auditory SOR will improve adaptive living skills at home, school, and in the community.

2. Background

There are limited approaches to specifically address auditory SOR in children with ASD. Exposure therapy (or systematic desensitization) may be a treatment option; researchers are investigating this approach. Many children receive sensory integration therapy, but this approach does not specifically target auditory SOR. Some families are advised to have their children avoid noxious stimuli or use compensatory techniques such as wearing headphones or ear plugs. While preliminary research suggests that use of noise attenuating headphones may reduce sympathetic activation for children with ASD and auditory SOR, this approach does not seek to change or alter the underlying cause of sympathetic activation (Pfeiffer et al., 2019). In addition, there is some concern that avoidance of sounds using ear plugs, noise canceling, or noise attenuating headphone can lead to increased anxiety and exacerbate the negative effects of hyperacusis (Juris et al., 2014).

Sound-based interventions are promising options to treat hyperacusis and subsequent auditory SOR in children with ASD. Over the years a variety of sound-based interventions, including music-based auditory stimulation and listening therapies, have been designed to reduce sound sensitivities including Tomatis-the Mozart Effect developed in the mid-20th century (Thompson & Andrews, 2000). According to Berard (1993), listening-based intervention that involved electronic modified music reduced maladaptive auditory processing and improved aspects of behaviors and learning. In 1997, the company Vital Links developed *Therapeutic Listening* and proposed the theory of relationship between sensory processing, brain and behavior. In 1998, the company Advanced Brain Technologies developed The Listening Program® and created Spectrum music in 2012 to improve auditory processing and reduce auditory sensory sensitivities. The company Integrated Listening Systems (ILS), founded in 2007, developed Safe and Sound protocol to reduce auditory sensitives.

Initial studies provide some support for sound-based interventions for children with ASD and auditory SOR. In 2014, Gee et al. conducted a case study to investigate changes in sensory processing, SOR, and auditory SOR-related behaviors for a 7 year-old child with ASD and auditory SOR after using The Listening Program® for 10 weeks. They noted a decrease in the number of negative and self-stimulatory behaviors during the study, but it was unclear if these

Modification / Update, MOD006-STU-2019-1698, [name], 4/12/2025

changes were due to The Listening Program® or the potential therapeutic effect of repeated exposure to one of the outcome measures – the Sensory Over-Responsivity Scales. Gee et al. (2015) used an ABAB design to study the effects of 10 weeks of The Listening Program® on three children with ASD and auditory SOR. There was a high variability of responses, but each child demonstrated an improved behavioral response during at least one phase of the study. Schoen et al. (2015) conducted a pilot study to explore the effects of Integrated Listening Systems Focus Series – another type of sound-based intervention – on seven children with sensory processing impairments after 8 weeks of intervention. They used a nonconcurrent AB design with a postintervention no treatment phase, and participants showed improvement in home and education related goals. Most participants also demonstrated changes in arousal level, as measured by parent report and the Sensory Challenge Protocol.

Our study will investigate the effects of a sound-based intervention developed in 2012 to specifically address the needs of children with ASD and children with hyperacusis and/or auditory SOR - The Listening Program® Spectrum music utilizing Waves™ (bone conduction) headphones by Advanced Brain Technologies. This program emphasizes low frequency music over an extended period of time; the duration recommended by Advanced Brain Technologies is 40 weeks. To our knowledge, this will be the first study investigating the effects of this specific program as well as the first study investigating the use of a sound-based intervention for 40 weeks for children with ASD and auditory SOR.

According to Advanced Brain Technology, The Listening Program ® Spectrum music requires a person listen to psycho-acoustically modified classical music online using specialized “Waves”™ headphones. The headphones transmit sound through bone conduction which provides another mode of perceiving sound (<https://advancedbrain.com>). The Listening Program ® can be carried out in the home environment with either the base schedule, two fifteen minute sessions at least 30 minutes apart, or a condensed schedule for 30 minutes.

The use of bone conduction was originally used for differential diagnosis between conductive and sensorineural hearing loss by using vibration on the mastoid bone to improve perception of sound (Allen, 2008). This technology started in the 19th century with the usage of the tuning fork and evolved to the bone conduction transducer during the 20th century (Stefan, Stenfelt, 2011). In the 1960’s, [name] created a method using bone conduction along with classical music to influence the vestibular system as well as the subcortical and cortical levels of the brain to deepen somatosensory awareness (Allen, 2008).

Bone conduction allows the listening experience to go deeper into the vestibular system which is purported to reduce stress, help regulate the “fight or flight” response, and allow the listener to achieve a state of calm and relaxed alertness. This theory is based on the function of the vagus nerve, the 10th cranial nerve, which has branches that extend to the eardrum. Stimulation of the vagus nerve stimulates the parasympathetic nervous system (Allen, 2008).

3. Concise Summary of Project:

Modification / Update, MOD006-STU-2019-1698, [name], 4/12/2025

Children with a diagnosis of ASD with auditory SOR to sound, ages 5 to 10 years, will be recruited from the campuses of Children's Health Rehabilitation and Therapy Services and the Center for Autism and Developmental Delays (CADD Clinic).

The study will use a nonconcurrent AB multiple baseline design, with A representing the baseline phase and B representing the intervention phase with a postintervention non-treatment phase. At baseline (A), demographic information will be collected and the following outcome measures will be completed: the Pediatric Evaluation of Disability Inventory Computer Adaptive Test with ASD Scales (PEDI CAT(ASD)), Sensory Processing Measure (SPM) home form, the Adaptive Behavioral Assessment System 3rd Edition ABAS-3 and Autism Treatment Evaluation Checklist (ATEC). During the intervention (B) phase, parents of participants in the treatment group will be educated by the investigators on use of The Listening Program at home, and then participants in this group will receive treatment at home utilizing The Listening Program for 40 weeks. Testing, using the same 4 outcome measures, will be completed at the 41st week after use, and then again after 3 months of no treatment. Between testing sessions, caregivers and investigators will set up three phone or hospital-approved virtual platform meetings at approximately 10 week intervals to check in and answer questions. The study is expected to run until the target number of 5 to 8 participants are enrolled.

4. Study Procedures:

Methodology: The caregivers of the children will meet with the principal or co-investigator for a 90-minute to 2-hour meeting. The meeting will include education on auditory SOR and the usage of the listening program and utilization of the wave bone conduction headphones for. All caregiver questions will be answered with caregivers verbalizing understanding of the research process, auditory SOR and equipment use. During this initial session, 4 questionnaire-based assessments, demographic information sheet and Consent to Participate in Research Form will be completed. A handout will be provided to the parent or caregiver which will include proper care, use and return of the "Waves"™ headphones and amplifier along with instructions to utilize the online listening system. Parents and caregivers will have the opportunity to ask questions and receive clarification about the study prior to signing the consent form.

The questionnaires based assessments include:

1. Adaptive Behavior Assessment System, Third Edition (ABAS-3)

[name], [name]

The third edition of this highly regarded assessment gives a complete picture of adaptive skills across the life span. Per the test manual, the ABAS-3 has good test-retest reliability ($r .72 - .84$ across all areas/domains). The ABAS-3 is easy to administer and score. It is particularly useful for evaluating those with developmental delays, autism spectrum disorder, intellectual disability, learning disabilities, neuropsychological disorders, and sensory or physical impairments (Harrison & Oakland, 2015). The ABAS-3 covers individuals from birth to 89 years of age (www.wpspublish.com/).

Modification / Update, MOD006-STU-2019-1698, [name], 4/12/2025

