The ATEC is a 77-item assessment tool developed at the Autism Research Institute. It was developed to provide a free, easily accessible, and valid tool to measure changes in ASD symptoms over time. The ATEC can be completed by parents, teachers, or others who see the individual’s behavior on a regular basis. The ATEC consists of four subtest scales: Speech/Language/Communication, Sociability, Sensory/Cognitive Awareness, and Health/Physical Behavior. The four subscale scores are used to calculate a total score (77 items – score range 0 to 180). A lower score indicates less severe symptoms of ASD and a higher score correlates with more severe symptoms of ASD. Baseline

Modification / Update, MOD006-STU-2019-1698, [name], 4/12/2025

scores can be compared with post-intervention scores to assist with determining intervention efficacy. Per data collected by the Autism Research Institute, Pearson split-half coefficients were calculated to examine the internal consistency. Subscale coefficients ranged from .82 - .92 and the total score coefficient was .94, indicating high internal consistency (Rimland & Edelson, 1999). Research shows the ATEC is highly correlated ($\rho = .71, p < .0001$) with the Childhood Autism Rating Scale (CARS), which is a widely used and well validated measure used to identify ASD (Geier et al., 2013), and there is some preliminary evidence that supports the use of the ATEC to monitor progress of children with ASD over time (Magiati et al., 2011).

The caregivers will be given a choice between a base schedule which includes two 15 minute sessions with at least 30 minutes in between sessions of listening per day for 5 consecutive days and two days off or a condensed schedule of one 30-minute session of listening per day for 5 consecutive days and two days off. A handout for the selected listening schedule will be given during the initial session.

Testing – using the same 4 questionnaire based assessments- will be completed at the 41st week after treatment these assessments, and then again after 3 months of no treatment. These visits are expected to take approximately 60 – 90 minutes, and the final visit may be completed in-person or using a hospital approved virtual platform. Between testing sessions for both groups, caregivers and investigators will set up three phone calls or hospital approved virtual platform meetings at approximately 10 week intervals to check in and answer questions.

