interested in having their child enrolled in the study.. If the child is eligible and the if the parents agree to have their child participate, a meeting at a Children's Health Specialty Center will be set. During this meeting, the study principal or co-investigator will complete the consent interview with the family. If the family agrees to participate after completing the consent interview and signs the informed consent form, the meeting will continue and the initial visit will begin.

10. Potential Risks:

This study poses no more than minimal risk to participants and their families. The questionnaire-based assessments used in the three data collection sessions are often administered by occupational therapists in pediatric rehabilitation settings, among other places, and are not known to cause any harm. Any adverse physical or psychological harm to study participants during the administration of Listening Program® Spectrum music with Waves™ (bone conduction) headphones is unlikely. The parent will have instructions on safe and appropriate usage of the Listening Program® at home, including recommendation to supervise their child during use and parents be in the line of sight of their child, how to don the headphones correctly (correct ear placement will be noted on the headphones), and how to accommodate fit of headphones for small children (e.g., using a headband or rolled up bandana to keep them in place). However, if the child is unattended while doing the Listening Program, possible risks include: chewing or otherwise tampering with the cord, moving the plug from the correct placement in the amplifier, raising the volume to an uncomfortable level, or discomfort due to headphones slipping out of place or placed backwards on the child's head. There may also be the risk of strangulation from the cord if the child is left unsupervised.

11. Subject Safety and Data Monitoring

During the three data collection sessions study participants will be asked to come to a Children's Health Specialty Center to fill out the 4 questionnaire-based assessments with the principal investigator or co-investigator. If preferred, parents can complete the final data collection session using a hospital approved virtual platform.

Given the nature of this study a Data Safety Monitoring Plan is not needed.

12. Procedures to Maintain Confidentiality:

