Statistical Analysis Plan: Descriptive analyses will be performed for the demographic and prognostic characteristics of the patients. Categorical variables will be reported with frequencies and proportions; continuous variables will be reported with means and standard deviations. The primary outcome is the ABAS-3 general adaptive composite score. The raw scores will be summarized in a box-and-whisker plot illustrating score distributions at baseline, at intervention and post intervention. Shapiro-Wilk and Kolmogorov Smirnov tests will be used to test whether the composite score follows normal distribution. If the composite score deviates significantly from normal distribution, transformation will be applied. Piecewise linear mixed-effects model could be used to model the score change over the 3 stages in the study. The statistical analyses will be performed with SAS version 9.4 (SAS Institute, Inc., Cary, NC).

References

Advanced Brain Technologies 6/2010 Certification course

Allen, S. (Dec. 2008) ABT Bone Conduction System Provider Reference Document

American Psychiatric Association: Diagnostic and Statistical Manual of Mental Disorders: Diagnostic and Statistical Manual of Mental Disorders, Fifth Edition. Arlington, VA: American Psychiatric Association, 2013.

Modification / Update, MOD006-STU-2019-1698, [name], 4/12/2025

- Berard, G. (1993). *Hearing and Behavior*. CT: Keats Publishing, Hearing equals behavior (pp 15-37)
- Harrison, P.L. & Oakland, T. (2015). *Adaptive Behavior Assessment System, Third Edition* [Manual], Torrance, CA: Western Psychological Services.
- <https://integratedlistening.com/about-ils/>

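### The study is labelled a multiple baseline design, but its schedule has one baseline ABAS-3 value per child and no stagger, so program effect and maturation cannot be separated

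*Combined protocol and SAP*

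**What the plan says.** Section 3 (Concise Summary of Project) names the design: "The study will use a nonconcurrent AB multiple baseline design, with A representing the baseline phase and B representing the intervention phase". It adds a no-treatment phase after the intervention.

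The measurement schedule is stated consistently in four sections:

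- **Baseline.** Section 4: "During this initial session, 4 questionnaire-based assessments, demographic information sheet and Consent to Participate in Research Form will be completed". The same meeting teaches the caregiver to use the program.
- **Later assessments.** Section 3: testing "will be completed at the 41st week after use, and then again after 3 months of no treatment".
- **Total.** Section 11: "During the three data collection sessions study participants will be asked to come". Section 14 likewise counts three phases per patient.

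The three check-ins at intervals of about 10 weeks are for contact and questions; no outcome is collected at them. The telephone screen in Section 9 asks only the 8 Hearing items of the SPM.

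On analysis, Section 14 says: "The primary outcome is the ABAS-3 general adaptive composite score", and "Piecewise linear mixed-effects model could be used to model the score change over the 3 stages in the study".

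On groups, Section 3 says that "parents of participants in the treatment group will be educated by the investigators", and Section 4 says: "Between testing sessions for both groups, caregivers and investigators will set up three phone calls". Neither section describes a comparison group, an allocation method or a control procedure, and Section 14 gives a single total of 8 patients.

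**The concern.** A multiple baseline design lets each child serve as his or her own control. Several pre-treatment values show where the child was heading, and starting treatment after baselines of different length shows whether change follows the start of treatment or simply the passage of time. Here phase A is a single point, no baseline duration or staggered start is given, and treatment follows the session at which that point is measured. Nonconcurrent entry varies only the calendar date, not the length of baseline.

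The children are 5 to 10 years old and are followed for about a year, so some development in adaptive skills is to be expected without any intervention. The Background says that the study will investigate the effects of the program, and nothing in the documents disclaims attribution. A reader who trusts the label could credit the results with a control over time trend that the data cannot supply. The stray references to groups strengthen the impression that a comparator exists.

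**Working it through.** There is no figure in the plan to reproduce on this point: Section 14 justifies 8 patients only by similarity to an earlier pilot of 7. The question is whether a program effect can be identified from the planned visits.

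**Inputs.** Visits at week 0 (Section 4) and week 41 (Section 3), and a third after 3 months without treatment, taken as 13 weeks, hence week 54 (an assumption). Sample size 5 to 8 (Section 3) or 8 (Section 14).

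**Step 1: the model as planned.** With columns 1, min(t, 41) and max(t − 41, 0), the matrix at three visits has rank 3 of 3. The model can be fitted and gives mean change over each stage.

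**Step 2: what the first slope means.** Add a column t for maturation:

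| Week t | Intercept | Maturation t | Treatment phase min(t, 41) | Post phase max(t − 41, 0) |
|---|---|---|---|---|
| 0 | 1 | 0 | 0 | 0 |
| 41 | 1 | 41 | 41 | 0 |
| 54 | 1 | 54 | 41 | 13 |

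The rank is 3 of 4. The null vector is (0, 1, −1, −1), because t = min(t, s) + max(t − s, 0) for any switch week s once every observation has t ≥ 0. Maturation is therefore exactly the sum of the two phase columns, whatever the number of children.

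**Step 3: does variation in timing help?** With an intercept for each child and visit weeks that differ between children (switch at week 40 to 44, follow-up 11 to 16 weeks later), the rank is 7 of 8 for n = 5 and 10 of 11 for n = 8. It is still one short. Measuring at weeks 10, 20 and 30 as well leaves the four-column matrix at rank 3. One ABAS-3 value before the start of treatment raises it to 4 of 4. The missing element is the repeated baseline.

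**Step 4: size of the ambiguity.** Each point of maturation over 41 weeks lowers the program estimate by one point with an identical fit. An illustrative observed rise of 6 points can be read as:

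| Program | Maturation | Fitted change |
|---|---|---|
| 6 | 0 | 6 |
| 4 | 2 | 6 |
| 2 | 4 | 6 |
| 0 | 6 | 6 |

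**Step 5: using the off phase as the control.** If the 3 months off treatment were pure maturation, the program effect over 41 weeks would be

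(Y41 − Y0) − (41/13)(Y54 − Y41) = −Y0 + 4.154·Y41 − 3.154·Y54.

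With independent, equal-variance errors, its variance in units of the error variance is 1 + 4.154² + 3.154² = 28.2, against 1 + 1 = 2 for simple change. The standard error ratio is √(28.2/2) = 3.76. It is 4.01 for an off phase of 12 weeks and 3.54 for 14 weeks.

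The estimate also depends heavily on the assumption. With no program effect and no maturation, a 2-point fall in the off phase produces a spurious program effect of 2 × 41/13 = 6.3 points; a 2-point rise produces −6.3.

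**The case against.** The strongest reply is that the plan does not promise what is being denied. The stated objective in the introductory section is to look at changes, Section 14 calls the study a pilot, the analysis is largely descriptive, the piecewise model is optional, and there is no efficacy hypothesis or significance level. The maturation column is an addition to the sponsor's model; without it the model is estimable. The effect could also be identified, either through the off-treatment phase or by letting age differences between children stand in for growth within a child, and age is collected. Finally, the size of any real maturation is not shown. If the analysed score is age-normed, expected drift could be small; Section 14 refers both to a composite score and to raw scores and does not settle this.

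Much of this is fair as far as it goes. The two-slope model can be fitted, a small pre-post pilot is a legitimate study, and the 6-point rise is only an illustration. But the added column does no more than show what the first slope contains. The two identifying assumptions are not stated in the plan; the first needs no carry-over or decay after treatment stops, and the second would rest on 5 to 8 children. Age-norming might shrink the expected drift, but it would not make the program effect identifiable. The design label remains a positive statement that the schedule contradicts.

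**Conclusion.** The concern holds. The label in Section 3 claims a design feature that the procedures in Sections 3, 4, 11 and 14 do not contain. Within-child change over the 41 weeks cannot be divided between program and maturation at any sample size unless an untested assumption is added. This conclusion does not depend on taking 3 months as 13 weeks or on placing the switch at week 41 rather than week 40. The standard error ratio of 3.8 (range 3.5 to 4.0) does depend on the length of the off phase and on independent, equal-variance errors. How much maturation would actually occur cannot be judged from the documents. The point limits what the trial may conclude; it does not make the pilot unworkable.

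**What to change.** 1. In Section 3, replace the design label with: single-arm pre-post pilot with one post-treatment follow-up.
2. In Sections 3 and 4, delete the wording that implies a treatment group and a second group, or define the second group if one is intended.
3. In Sections 3 and 14, state that change from baseline in the ABAS-3 composite, including any slope from the piecewise model, is descriptive and cannot be attributed to the program as distinct from maturation, other therapies or caregiver expectation. The last two follow from the same lack of a comparator: the caregivers who supervise the sessions also complete the questionnaires.

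This costs wording only: no visits, forms, participants or staff. The price is a more modest claim.

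If the sponsor wants to keep the label, the alternative is to specify repeated baseline ABAS-3 values with staggered starts and to name the model term that carries the program effect. That costs extra assessments and would bring little precision. In an illustrative layout of 8 children with 3, 5 or 7 baseline values two weeks apart, the rank is 4 of 4. However, the standard error of the 41-week effect is about 2.3 residual SDs, against √(2/8) = 0.5 for simple change. Section 12 speaks of participant codes as already assigned, so this route may be closed for children already enrolled.
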